8.5 Investigation Device(s) and Comparators

All patients will receive standard post-operative wound follow up. This might include being advised to contact the GP or the hospital if there are any wound problems and, or, being invited to an out-patient clinic appointment. Patients in the intervention group will have their wounds monitored remotely – they do this by taking images of their wound using their phone which they submit online along with responses to the modified UKHSA SSI post-discharge questionnaire. The new wound prioritisation module which is under investigation is incorporated within the digital monitoring platform and flags images for the clinical for urgent review.

9.0 PHARMACOVIGILANCE

9.1 Definitions

Term	Definition						
Adverse Event (AE)	Any untoward medical occurrence, unintended disease or injury, or						
	untoward clinical signs (including abnormal laboratory findings) in						
	subjects, users or other persons, where or not related to the						
	investigational medical device and whether anticipated or						
	unanticipated.						
Adverse Device	An adverse event related to the use of an investigational medical						
Effect (ADE)	device.						
	 NOTE: this definition includes: AEs resulting from insufficient or inadequate instructions for use, deployment, implantation, installation, or operation, or any malfunction of the investigational medical device. Any event resulting from use error or from intentional misuse of the investigational medical device. 						
	Comparator' if the comparator is a medical device.						
Serious Adverse Event (SAE)	 An adverse event that led to any of the following: death serious deterioration in the health of the subject, users, or other persons as defined by one of more of the following a life-threatening illness or injury, or a permanent impairment of a body structure or a body function including chronic diseases, or in-patient of prolonged hospitalisation, or 						

	 medical or surgical intervention to prevent life-threatening
	illness or injury, or permanent impairment to a body structure
	of a body function,
	 foetal distress, foetal death, a congenital abnormality, or birth defect
	including physical or mental impairment.
	NOTE: Planned hospitalisation for a pre-existing condition, or a
	procedure required by the CIP without a serious deterioration in health,
	is not considered a SAE.
Serious Adverse	An adverse device effect that has resulted in any of the consequences
Device Effect (SADE)	characteristic of a serious adverse event.
Unanticipated	A serious adverse device effect which by its nature, incidence, severity or
Serious Adverse	outcome has not been identified in the current risk assessment.
Device Effect	
(USADE)	NOTE: Anticipated serious adverse device effect (ASADE) is an effect which by
(,	its nature, incidence, severity or outcome has been identified in the risk
	assessment.
Device Deficiency	Inadequacy of a medical device with respect to its identity, quality, durability,
,	reliability, usability, safety or performance.
	NOTE: This definition includes:
	• Malfunctions, use errors, and inadequacy in the information supplies
	by the manufacturer including labelling.
	• Device deficiencies related to the investigational medical device or the
	comparator.
Serious Health	Signal from any adverse event or device deficiency that indicates an imminent
Threat	risk of death or a serious deterioration in the health in subjects, users or other
	persons, and that requires prompt remedial action for other subjects, users or
	other persons.
	NOTE: this would include events that are of significant and unexpected nature
	such that they become alarming as a potential serious health hazard or
	possibility of multiple deaths occurring at short intervals.
Recording*	Information collected and transcribed to the participant's eCRF
Reporting*	Expedited to the MHRA and REC via the applicable forms listed in section 9.3.

*Only In the context of safety information / data

9.2 Operational Definitions for (S)AEs

The intervention in this study is an AI module for a wound monitoring platform designed to flag wound images for priority review. As all patients will receive standard wound care follow up we do not expect there to be any adverse events caused by the device that will affect patients. If the new wound prioritisation module does not work, then the clinician may review a patient's wound image within two days rather than one day. This is still faster than standard wound care follow up.

The following events are expected adverse events following surgery and will be recorded in the eCRF but not expedited to the Sponsor .

- Patent develops a surgical site infection (around 8%)- record in medical notes and eCRF,
- Patient is readmitted to hospital because of a wound infection record in medical notes and eCRF
- Patient requires further surgery to debride wound infection record in medical notes and eCRF
- Patient develops sepsis as a result of a wound infection record in medical notes and eCRF

The following event is a foreseeable expected serious adverse event following surgery which will be recorded and also reported to the sponsor ([contact]),

- Patient dies following a wound infection record in medical notes and eCRF and report
- Any patient death and cause record in medical notes and eCRF and report

The following events are possible device deficiencies that may arise from using an AI module to prioritise non-healing wounds. These are unlikely to lead to an adverse event as all images will be assessed by a clinician. These will not be reported to the Sponsor but will be recorded:

- The module fails to identify a non-healing sign and does not prioritise a wound for urgent review record in medical notes and eCRF document for research data only, participant's image will still be reviewed routinely,
- The module identifies a healing wound that does not require prioritise review record in medical notes and eCRF document for research data only.

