9.3 Recording and Reporting Safety Information

All AEs, SAEs and device deficiencies must be recorded from the time of written informed consent until after the last visit.

All AEs and device deficiencies occurring during the duration of the study must be recorded in patients' medical notes and within the eCRF. The PI is responsible for checking for device deficiencies, A(D)Es and SA(D)Es when participants attend for treatment and follow-up.

- The following events are considered reportable to the MHRA (using the MEDDEV 2.7/3 SAE reporting table) and REC (via the Non-CTIMP safety report to REC form). Any SAE (whether initially considered device related or not)
- Any device deficiency that might have led to a SAE if:
 - Suitable action had not been taken or
 - Intervention had not been made or
 - If circumstances had been less fortunate.
- New findings/updates in relation to already reported events

All reportable events must be first recorded by the investigator using the applicable CTU's SAE/SADE/Device deficiency reporting form and submitted to the Derby CTSU within 24 hours of the research team becoming aware of the event; even if not all information is available at the time (further information should be provided on the CTU's Safety Follow Up Report Form). Any change of condition or other follow-up information should be sent to the CTU as soon as it is available, or at least within 24 hours of the information becoming available. Events will be followed up until the event has been

resolved or a final outcome has been reached. Safety information will be reviewed during trial management group meetings.

Derby CTSU contact information:

Email: [contact].

[contact] or [name] (must be followed up with a written report).

For each reportable event the following information will be collected as a minimum:

- Full details of the event, including a diagnosis
- MedDRA coding (system organ class and preferred term)
- Duration (start and end dates)
- Seriousness criteria
- Outcome.
- Action taken.
- Causality (*i.e.* related to investigational medical device)
- Expectedness

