9.3.2 Expedited safety reporting

For trials of investigational medical devices that are non CE-marked all reportable events must be reported to the MHRA using the MEDDEV 2.7/3 SAE reporting table (or MDCG 2020-10/2 SAE reporting table) via the MORE portal and the manufacturer. All events which indicate an imminent risk of death, serious injury, or serious illness that requires prompt remedial action for patients, users or other persons should be reported to the MHRA within 2 calendar days of Sponsor awareness. Any other reportable events must be reported within 7 calendar days of awareness by the Sponsor. In addition, all USADEs must be reported to the REC.

In addition to the reporting of individual serious adverse events as detailed above, quarterly summary reports of all serious adverse events will also be provided (Items I, II & III in tabular format) and should include the following:

- I. number of serious adverse events
- II. number of participants affected by those events
- III. percentage of the total number of enrolled participants affected by those events
- IV. A summary analysis of the serious events together with the manufacturer's conclusions

The first quarterly report should be submitted the first quarter after the first patient has been treated. The SAE reporting form should be submitted via https://more.mhra.gov.uk/login. All reporting to MHRA will be coordinated by Derby Clinical Trials Unit with assistance from ISLA.

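### Section 9.2 withholds from the sponsor wound-infection events and missed red flags that sections 9.1 and 9.3 can make reportable

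*Protocol*

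**What the plan says.** Section 9.2 gives three lists.

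- **Expected adverse events.** The rule is "The following events are expected adverse events following surgery and will be recorded in the eCRF but not expedited to the Sponsor". Besides surgical site infection itself (around 8%), the list contains "Patient is readmitted to hospital because of a wound infection", "Patient requires further surgery to debride wound infection" and "Patient develops sepsis as a result of a wound infection".
- **Expected serious adverse events, recorded and also reported to the sponsor.** This list contains only deaths.
- **Possible device deficiencies.** These are a non-healing sign that the module misses and a healing wound that it flags unnecessarily. The rule is "These will not be reported to the Sponsor but will be recorded", and both entries are described as research data only.

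Section 9.1 defines a serious adverse event. Among its criteria is "in-patient of prolonged hospitalisation, or" (evidently meaning in-patient or prolonged hospitalisation). Others are life-threatening illness, and medical or surgical intervention to prevent such illness or permanent impairment.

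Section 9.3 lists what is reportable to the MHRA and REC. The first entry is "Any SAE (whether initially considered device related or not"). The list also includes device deficiencies that might have led to an SAE had action, intervention or luck been different. The investigator's form goes to Derby CTSU within 24 hours.

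Section 9.3.2 sets the MHRA deadlines at 2 or 7 calendar days, counted from the sponsor's awareness, and adds: "In addition, all USADEs must be reported to the REC".

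**The concern.** A site has two instructions for the same event. Under 9.2, a patient readmitted with an infected wound is an expected adverse event to be entered in the eCRF. Under 9.1 and 9.3, the same readmission is an SAE that needs a form within 24 hours and a report to the MHRA and REC. Nothing in either section says which prevails.

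These events matter for this device. In the intervention arm, a wound infection that progresses to readmission, debridement or sepsis is how a missed or delayed flag could harm a patient. The missed flag itself is the deficiency that 9.2 sets aside as research data. If both are handled under 9.2 alone, the event and its possible cause can each go without the assessment that 9.3 requires. Safety is among the study's primary objectives, so this is more than a drafting matter.

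**Working it through.** The point rests on comparing the text. No sample-size, power or alpha figure is involved.

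**Step 1: are the 9.2 events serious under 9.1?**

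| Event in 9.2 | Criterion in 9.1 | Result |
|---|---|---|
| Surgical site infection alone | None necessarily | Need not be serious |
| Readmission for wound infection | Hospitalisation | Serious outright |
| Surgery to debride | Hospitalisation, or intervention to prevent life-threatening illness or permanent impairment | Usually serious, not automatically |
| Sepsis from wound infection | Hospitalisation or life-threatening illness | Usually serious, not automatically |

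The only exemption in 9.1 covers planned hospitalisation for a pre-existing condition, or a procedure that the plan itself requires, without serious deterioration in health. Readmission for a wound infection is neither.

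**Step 2: does any later section exempt expected events?** No.

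- 9.3 covers any SAE, whatever its initial relation to the device, and does not refer to the 9.2 list.
- 9.3.1.1 says that a change making a non-serious event serious is to be reported as a new serious event. An infection that later leads to readmission fits that description.
- 9.3.1.3 requires expectedness to be assessed only for device-related events. It is not a route out of reporting for surgical complications.
- 9.3.2 sends all reportable events to the MHRA for devices without a CE mark.
- 9.4, on pregnancy, repeats that an event meeting an SAE criterion has to be reported as one.
- The amendment history records no change that settles the matter.

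**Step 3: device deficiencies.** 9.2 excludes missed non-healing signs from sponsor reporting as a class. 9.3 requires a case-by-case test of whether the deficiency might have led to an SAE. A missed sign on a wound that is in fact infected is an obvious candidate for that test. The causality criteria in 9.3.1.2 also name dependence on a false result from the device. The class exclusion pre-empts both assessments.

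**Step 4: REC wording.** 9.3 sends every SAE to the REC. 9.3.2 says that USADEs must go to the REC. USADEs are a subset of SAEs, so the second sentence is redundant if the first applies, and ambiguous if it was meant to narrow it.

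**Step 5: how often could the clash arise?** Inputs are the 8% infection rate (Trial Summary and section 11.1), 120 patients in total and 60 per arm.

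- Infections per arm: 60 × 0.08 = 4.8, which agrees with the 4 to 5 per group in the Trial Summary.
- Infections in total: 120 × 0.08 = 9.6.

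The protocol does not give the share *s* of infections that lead to readmission, debridement or sepsis. The values of *s* below are assumptions. Expected patients = 9.6 × *s*; probability of at least one = 1 − (1 − 0.08*s*)^120.

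| Assumed *s* | Expected patients | Probability of at least one |
|---|---|---|
| 10% | 0.96 | 1 − 0.992^120 = 62% |
| 25% | 2.4 | 1 − 0.98^120 = 91% |
| 50% | 4.8 | 1 − 0.96^120 = 99% |

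Under these assumptions the clash is likely to arise at least once. The table counts occasions for the clash, not unreported SAEs.

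**The case against.** The strongest defence is that the recipients differ. 9.2 speaks of the sponsor, 9.3 sends the form to Derby CTSU, and 9.3.2 has the trials unit coordinate reporting to the MHRA. A site could send the form to the unit, not expedite to the sponsor, and comply with both sections literally. That is fair as a literal reading, but it does not remove the conflict. The MHRA deadlines in 9.3.2 run from sponsor awareness, the unit acts under the sponsor's delegation, and 9.2 puts only deaths in its serious category. A site would naturally read it as saying that no SAE form is due for the other events.

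A second defence is that the flow chart in Appendix 2, which could not be read in the available text, may show the routing. If so it would help sites, but the sections would still disagree with each other.

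Several stronger readings are tempting and are not supported:

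- A reader might infer that these events would vanish from the quarterly SAE summary and from steering committee review. 9.3.2 requires that summary to cover all SAEs, 9.2 puts every listed event in the eCRF, and the committee's safety review is not limited to expedited reports.
- A reader might infer that the arms could not be compared. All adverse events are recorded and tabulated, readmissions and further surgery are sought by case-note review for every patient, and randomisation is stratified by site.
- A reader might infer that 9.3.2 restricts REC reporting to USADEs. It contains no such restriction.
- For missed flags, 9.3 reaches only those that might have led to an SAE, and 9.2 presumes that such deficiencies are unlikely to cause harm. The conflict concerns that subset, not every missed flag.

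**Conclusion.** The contradiction stands as written and should be corrected. Readmission for wound infection is an SAE under 9.1, and debridement and sepsis usually will be. 9.2 says that these are not expedited to the sponsor, while 9.3 makes any SAE reportable without exception. The same conflict applies to missed non-healing signs that might have led to an SAE. A site following 9.2 could fail to submit reportable SAEs and deficiencies.

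The size cannot be derived from the protocol. About 9.6 infections are expected at 8%, but the share that becomes serious is not stated. A reader might turn this into a count of missing SAEs. That would need an assumed share and would also need sites to disregard 9.3, and the documents support neither. Roughly half of the infections would also fall in the control arm, which does not use the module, so not every such event bears on device harm. The conclusion depends on none of these figures.

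**What to change.** Reconcile 9.2, 9.3 and 9.3.2 into one reporting rule.

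1. State that any event on the 9.2 list that meets the 9.1 SAE definition follows 9.3, or document an explicit exemption agreed with the regulator and refer to it in 9.3. Which of the two applies is for the sponsor and the regulator to settle.
2. State that each missed red flag is assessed against the 9.3 test of whether it might have led to an SAE, and is handled according to the result.
3. Align the REC wording in 9.3 (all SAEs) and 9.3.2 (USADEs) so that one rule remains.
4. Confirm that events meeting the SAE definition are counted in the quarterly summary that 9.3.2 already requires. No new table is needed.
5. Check that the flow chart in Appendix 2 shows the same rule.

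The cost is a protocol amendment, a memo to the two sites and a few extra SAE forms. The design, sample size and analysis do not change.

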9.4 Pregnancy reporting

It is unlikely, but possible, that pregnant women will be undergoing coronary artery bypass graft surgery. Due to the non-invasive nature of the study – taking a digital photo of a surgical wound and answering questions about a surgical wound, it is not deemed necessary to notify the CTU of pregnant

participants or follow them up until the outcome of the pregnancy. As per standard reporting criteria, if at any stage an event occurs that meets the criterion for an SAE then it must be reported as such.

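### Section 9.2 exempts wound-infection readmission, debridement surgery and sepsis from expedited reporting, while 9.1 and 9.3 together make such events reportable when they are serious

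*Protocol*

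**What the plan says.** Protocol section 9.2 opens a list with "The following events are expected adverse events following surgery and will be recorded in the eCRF but not expedited to the Sponsor". Besides surgical site infection itself, the list holds three items. The one on readmission reads "Patient is readmitted to hospital because of a wound infection record in medical notes and eCRF". The other two, a repeat operation for debridement and sepsis arising from the infection, carry the same recording instruction. A separate list in 9.2, of foreseeable serious events that are reported to the Sponsor, contains only deaths.

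Section 9.1 counts in-patient or prolonged hospitalisation, life-threatening illness, and medical or surgical intervention to prevent life-threatening illness or permanent impairment as SAE outcomes. It excludes only planned hospitalisation for a pre-existing condition and procedures that the plan itself requires.

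Section 9.3 names as reportable to the MHRA and REC "Any SAE (whether initially considered device related or not", and requires a form to reach the Derby trials unit within 24 hours of the team becoming aware. The content of that report is introduced by "For each reportable event the following information will be collected as a minimum"; the list includes MedDRA coding, seriousness criteria, causality and expectedness. Section 9.3.2 sends reportable events to the MHRA and says "Any other reportable events must be reported within 7 calendar days of awareness by the Sponsor", with a shorter limit of 2 days for imminent serious risk. Section 9.4, on pregnancy, restates the general rule: "if at any stage an event occurs that meets the criterion for an SAE then it must be reported as such".

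**The concern.** The same event gets two different instructions. A patient readmitted with an infected wound is, under 9.2, an entry in the notes and eCRF and nothing more. Under 9.1 and 9.3 that patient has an SAE needing a form within 24 hours and a report to the MHRA and REC.

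The affected events matter for this device. The module is meant to bring worrying wound images forward for urgent review. If a missed flag delayed treatment, the harm would be expected to show as a worse infection, with readmission, further surgery or sepsis. A site relying on 9.2 could leave these events out of the route by which the trials unit, Sponsor and regulator would hear of them promptly.

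**Working it through.** **Step 1. Do the listed events meet the SAE definition in 9.1?**
- Readmission for wound infection: yes, directly. It is in-patient hospitalisation, and neither exclusion in 9.1 applies to an unplanned readmission.
- Sepsis: usually, as a life-threatening illness, but on case judgement.
- Debridement surgery: usually, as a surgical intervention to prevent a serious outcome, also on case judgement.
- Surgical site infection alone: not necessarily.

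**Step 2. Does 9.3 carve out expected SAEs?** No. It covers SAEs whether or not they are thought device related. Expectedness in 9.3.1.3 is assessed only for device-related events, so being expected after surgery in the sense of 9.2 creates no exemption. The note in 9.3.1.1 points the same way: an event that moves from not serious to serious should be reported as a new serious event.

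**Step 3. Could recorded but not expedited still mean reported?** Not on the protocol's own terms. Section 9.1 defines recording as entry in the eCRF and reporting as expediting to the MHRA and REC.

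**Step 4. What do 9.3.2 and 9.4 add?** They are consistent with 9.3 but are not independent rules. Section 9.3.2 uses the term reportable as 9.3 sets it, and 9.4 repeats the standard criterion. Section 9.3.2 does supply the starting point of the MHRA clock, which is Sponsor awareness.

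**Step 5. What could be lost if a site follows 9.2?** The 24-hour form with its minimum dataset, and a timely start of the clock.

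**Step 6. How many events?** Inputs: infection rate 8% (Trial Summary, 9.2 and 11.1); 120 patients, 60 per group (11.1).
- Plan's own figure: 60 × 0.08 = 4.8 infections per group, which agrees with the 4 to 5 in the Trial Summary.
- Whole trial: 120 × 0.08 = 9.6 infections.
- The share of infections leading to readmission, debridement or sepsis is not in the documents. Assume 20% to 50%.
- Whole trial: 9.6 × 0.20 = 1.9 to 9.6 × 0.50 = 4.8 events.
- Intervention arm, the only one where a flag can be missed: 4.8 × 0.20 = 0.96 to 4.8 × 0.50 = 2.4 events.
- Chance of at least one such event in the trial: 1 − (1 − 0.08 × 0.20)^120 = 1 − 0.984^120 = 86%, to 1 − (1 − 0.08 × 0.50)^120 = 1 − 0.96^120 = 99%.

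On this assumption the conflict will probably arise in practice.

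**The case against.** The strongest reply is that little is lost. Section 9.3 requires all adverse events and SAEs to be recorded and makes the principal investigator responsible for checking for serious events and device effects. Section 9.3.1.2 asks for the relationship to the device to be judged for each adverse event, by a medically qualified doctor. Section 11.8 tabulates adverse events and adverse device effects. Readmissions and further surgery are also sought for every patient in the 60-day case-note review. This stands. A reader might infer that these events would go without any causality assessment, or would be neither identified nor counted; the documents do not support that. What 9.2 puts at risk is the individual expedited report.

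A reader might also infer that the quarterly SAE totals must be too low. Section 9.3.2 asks for summaries of all SAEs, and these events are in the eCRF. The totals would fall short only if sites also took 9.2 to class the events as non-serious. That reading is open, because the serious list in 9.2 contains only deaths, but it is not certain.

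A further reply is that 9.2 speaks only of the Sponsor, whereas the 24-hour form goes to the Derby trials unit, which manages the project by delegation and coordinates MHRA reporting. It is therefore too strong to say that 9.2 stops the clock. But nothing visible says that the 9.2 events still go on that form, so the ambiguity remains. The safety reporting flow chart in Appendix 2 is not legible in the copy reviewed and might clarify the routing; it would not remove the conflict in the text.

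**Conclusion.** This is an internal inconsistency that has to be corrected. The conflict is certain for unplanned readmission and usual, subject to case judgement, for sepsis and debridement. The consequence is limited to an omitted or late individual report, the loss of that report's minimum dataset, and a possibly late start of the MHRA clock. Recording in the notes and eCRF and the causality judgement for each adverse event remain in force.

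The size, about 1.9 to 4.8 events overall and 1.0 to 2.4 in the intervention arm, rests on the protocol's 8% and on an assumed serious share of 20% to 50%. Only the intervention-arm figure bears on harm from a missed flag. The contradiction itself does not depend on either range.

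**What to change.** Reconcile 9.2 with 9.1 and 9.3 by one of two routes:
- limit the 9.2 list of events that are not expedited to those that do not meet the SAE definition in 9.1, and send the others through the 9.3 form; or
- if an exemption has been agreed with the regulator, state it in 9.3, and keep the capture of seriousness and causality for these events in both arms.

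In either case, say in 9.2 whether these events go to the trials unit, the Sponsor or both, and check that Appendix 2 agrees. Align the REC rules too: 9.3 sends all reportable events to the REC, whereas 9.3.2 names only unanticipated serious adverse device effects.

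The cost is a wording amendment, handled under 13.8, and site retraining. If the first route is taken, there would also be roughly two to five extra SAE forms on the assumption above.
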